2. Evaluate the progress of the trials, participant recruitment, accrual and retention, participant risk versus benefit, and other factors that can affect study outcome;
3. Protect the safety of the study participants and review interim or cumulative data for evidence of adverse events;
4. Review safety and progress report from an unblinded statistician who will use both blinded and unblinded data;
5. Make recommendations to the institutions involved and the PIs concerning continuation, termination or other modifications of the trials based on the observed beneficial or adverse effects of the treatment under study;
6. Review report on interim analysis of efficacy in accordance with stopping rules which are clearly defined in advance of data analysis and have the approval of the DSMB;
7. Ensure the confidentiality of the trial's data and the results of monitoring; and
8. Review issues that have been identified by the study team and upon request by the study team, review problems that are identified by the monitors in relation to patient safety.

DSMB Recommendations

The DSMB may conclude each review with recommendations to continue the trial without change, modification of the trial, or termination of the trial based on pre-defined criteria established at the beginning of the trial.

Recommendations for modification of the design and conduct of the trial may include:

1. Modifications of the study protocol based upon the review of the safety data;

2. Suspension or early termination of the study because of serious concerns about subjects' safety, inadequate performance or rate of enrollment;
3. Suspension or early termination of the study because study objectives have been obtained according to pre-established statistical guidelines;
4. Optional approaches for trial design when the DSMB determines that the incidence of primary study outcomes is substantially less than expected, such as recommendations to increase the number of trial centers or extend the recruitment period/follow-up period; and,

Confidentiality

Confidentiality will be maintained during all phases of DSMB review and deliberations. Only voting members of the DSMB will have access to interim analyses of outcome data by treatment group. Exceptions may be made when the DSMB deems it appropriate. DSMB members must maintain strict confidentiality concerning all privileged trial results ever provided to them. The DSMB will review data only by masked study group (such as 'Intervention 1' versus 'Intervention 2' rather than cryotherapy versus LEEP) unless the DSMB determines that the identities of the groups are necessary for their decision-making. Any request to unmask data must be made in writing.

Membership

The DSMB will be composed of four members chosen from both the U.S. and Kenya.

The members include:

1. R. [name], MPH, Associate Professor of Medicine, Epidemiology and Global Health, UW;
2. [name], Associate Member, FHCRC, Research Associate Professor, Department of Biostatistics, UW;

3. [name], MMed, MPH, Professor of Obstetrics/Gynecology, KNH; and
4. [name], Professor, Women's Health, Chairman, Department of Obstetrics and Gynecology, UW
5. *Ad hoc* specialists may be invited to participate as non-voting members at any time if additional expertise is desired.

Meetings

The first meeting will take place either prior to trial initiation or early after the trial has been initiated to discuss the protocol. A designated DSMB member and the PIs will prepare the agenda to review initiation of the trial and reporting of adverse events. The DSMB will also review monitoring guidelines and approve or give recommendations..

Once the trial has been initiated, the DSMB will meet, as outlined above, to examine the accumulated safety and enrollment data, review study progress and discuss other factors (internal or external to the study) that might impact continuation of the trials as designed. A DSMB meeting may be requested by DSMB members or the Principal Investigators at any time to discuss safety concerns, and includes the occurrence of any Significant Adverse Event (SAE) that is associated with the study. The study team will provide the logistical management and support of the DSMB meetings. The meetings will be convened by teleconference to decrease travel cost. An emergency meeting of the DSMB may be called at any time should questions of patient safety arise.

Meeting Format

The meetings will mainly be open sessions. These sessions will be attended by the Principal Investigators or designee. Other research staff may attend the open sessions but this is up to the discretion of the PI. Issues discussed at open sessions will include conduct and

progress of the study, including patient accrual, compliance with protocol, and problems encountered. Patient-specific data and treatment group data will not be presented in these sessions.

Closed sessions may be requested by the DSMB at any time and will be attended by voting DSMB members and the unblinded statistician. Any other trial staff may be requested to attend by the DSMB. All safety and efficacy data will be presented at this session. The discussion at the closed session is completely confidential.

Should the DSMB decide to issue a termination recommendation, the full vote of the DSMB will be required. In the event of a split vote, majority vote will rule and a minority report will be appended. An appeal may be filed by study PIs if a termination decision is made.

Study Stopping Criteria

The DSMB may recommend stopping the study for the following reasons:

- The data show a significantly increased risk of serious adverse effects in one of the treatment arms.
- Interim efficacy analyses show significant treatment benefits or futility in the one treatment group. The interim efficacy analyses are based on pre-specified stopping boundaries for the primary endpoint of the study which preserve the study wide Type I error rate.
- It becomes clear that successful completion of the study is not feasible (e.g. there is an excess of patient dropout, missing data, lack of recruitment etc).

Interim Efficacy Analyses

This study will employ interim analyses to assess accumulating study data for early evidence of treatment efficacy. The primary outcome, recurrence of cervical intraepithelial neoplasia grade 2 or 3, will be compared between groups at the following approximate times: months 9, 15, 21 and 27, and for DSMB safety, upon cumulative enrollment and intervention of 100 patients. The decision criteria for stopping the study at each interim analysis are based on O'Brien-Fleming superiority boundary with Type I error controlled at alpha-level $\alpha = 0.05$. In the event that interim analyses are conducted at times other than the preplanned times (e.g. unequal information accrual) the stopping criteria will be adjusted to maintain overall type I error rate of $\alpha = 0.05$. We will use Lan-DeMets alpha spending approach, to make the necessary adjustments. The decision criteria for stoppage are based on a power of 80% to detect a treatment group difference at the end of study.

Report

A formal report prepared by an assigned administrator will be reviewed and approved by the DSMB chair, who will prepare a summary. The minutes and summary will be sent to the full DSMB within three weeks of the meeting. Once approved by the DSMB, the chair of the DSMB will sign on behalf of the board and the report will be forwarded to the participating institutions within 4 weeks of each meeting. The PIs will submit the results of these meetings to the UW Institutional Review Board (IRB), the KNH Ethics Review Committee (ERC), and the Centers for Disease Control (CDC) which is the study sponsor. Each report will conclude with a recommendation to continue or to terminate the study. This recommendation will be made by formal majority vote. A termination recommendation may be made by the DSMB at any time by majority vote. The report will not include un-blinded data or any discussion of the un-blinded data.

Any new findings discovered by the DSMB during the course of the study that may affect the willingness of subjects to remain in the study will be shared by the study doctor or nurse through direct discussions and printed pamphlets.

Sponsor Monitoring

As the study sponsor, the Centers for Disease Control (CDC) may conduct monitoring or auditing of study activities to ensure the scientific integrity of the study and to ensure the rights and protection of study participants. Monitoring and auditing activities may be conducted by:

- CDC staff (“internal”)
- authorized representatives of CDC (e.g., a contracted party considered to be “external”)
- both internal and external parties

Monitoring or auditing may be performed by means of on-site visits to the Investigator’s facilities or through other communications such as telephone calls or written correspondence. The visits will be scheduled at mutually agreeable times, and the frequency of visits will be at the discretion of CDC. During the visit, any study-related materials may be reviewed and the Investigator along with study staff should be available for discussion of findings.

The study may also be subject to inspection by regulatory authorities (national or foreign) as well as the IECs/IRBs to review compliance and regulatory requirements.

Acronyms

AIDS – Acquired Immunodeficiency Syndrome

CCSP – Cervical Cancer Screening Program, Coptic Hope Center for Infectious Diseases

CDC – Centers for Disease Control

CIN – Cervical Intraepithelial Neoplasia

CIS – Carcinoma in situ

CVL – Cervicovaginal Lavage

HIV – Human Immunodeficiency Virus

HPV – Human Papillomavirus

IRB – Institutional Review Board

KNH – Kenyatta National Hospital

LEEP – Loop Electrosurgical Excision Procedure

OGAC – Office of the Global AIDS Coordinator

Pap – Papanicolaou

PEPFAR – President’s Emergency Plan for AIDS Relief

PHE – Public Health Evaluation

RNA – Ribonucleic Acid

UNITID – University of Nairobi Institute of Tropical and Infectious Diseases

UoN – University of Nairobi

USA – United States of America

USG – United States Government

UW – University of Washington

VIA – Visual Inspection with Acetic Acid

ENROLLMENT

Study ID Number ___ ___ **Hope ID Number** ___ ___ **Interviewer Number** ___

Date of interview (day/month/year) ___ ___ / ___ ___ / ___ ___

Agreed to store samples: Yes No Don't know Other, specify

A: SOCIODEMOGRAPHIC

1. Date of birth (day/month/year) ___ ___ / ___ ___ / ___ ___

2. Age _____ years

3. How many years of education did you complete? _____ years

4. What is highest education level you have completed? None

Primary

Secondary

Higher education/ University

Don't know

Refused

Other, specify

5. Marital status (tick one): Married (monogamous)

Married (polygamous)

Single

Divorced/Separated

Widowed

Refused

Cohabiting

Other, specify

6. Employment (tick one): Salaried job

Self-employed

- Housewife
- Unemployed
- Casual laborer
- Refused
- Other, specify

7. Household income per month (tick one): None
- < 5000 Ksh
- 5001 – 10000 Ksh
- 10001 – 15,000 Ksh
- >15,000 Ksh
- Don't know
- Refused

B: SEXUAL HISTORY

8. How old were you when you first had vaginal intercourse? ___ ___ Don't know
 refused never Other, specify
9. How many sex partners have you ever had? ___ ___ Don't know refused
 Other, specify _____
10. How many different sex partners did you have in the last year? ___ ___
 Don't know refused Other, specify
11. Have you had sex in the last month? (If no, don't know, refused, skip to 14)
 Yes No Don't know Refused Other, specify
12. How often have you used condoms during sex in the last month?
 Always (100%) Most of the time (75-99%)
 Half of the time (50%-74%) Sometimes (25-49%)

 Rarely (1-25%) Never (0%)
 Refused
 Don't know Other, specify
13. Do you think you may be currently pregnant? Yes No Don't know
 Refused Other, specify

C: CERVICAL CANCER SCREENING HISTORY

14. Have you been previously screened for cervical cancer? Yes No

Don't know Refused Other, specify

If no, don't know or refused skip to 20.

15. What cervical cancer screening test did you undergo most recently (tick one)?

Pap smear

Visual inspection with Acetic acid

HPV

Other, specify: _____

Don't know

Refused

16. Where was the most recent test performed?

Coptic

KNH

Refused

Don't know

Other, specify

17. When was the test performed?

Don't know

18. What were the results?

Normal

Abnormal, specify _____

Don't know

Refused

19. Did you receive any cervical treatment or surgery as a result of this test?

Yes No Don't know Refused Other, specify _____

If yes, specify _____

20. Was Pap Smear performed today? Yes No
 If no, explain Refused Don't know
21. Comments.

PAP SMEAR

Study ID Number _____

Interviewer Number _____

Date of interview (day/month/year) ____/____/____

Visit (tick one) Initial Visit Repeat Month 6 FU Month 12 FU Month 18 FU Month 24 Other, specify _____

A: PHYSICAL EXAMINATION

1. Temperature _____°C
2. Is there inguinal node enlargement Yes No
3. Is there abdominal tenderness Yes No
4. Are there any abdominal masses Yes No
5. Were there any other abnormalities found on general physical exam Yes No
If yes, specify _____

B: PELVIC EXAMINATION

6. What was found on the external genital exam (tick all that apply)?

 Abnormal visible discharge at introitus	 Ulcers
 Excoriations	 Vesicles
 Oedema	 Papules
 Sores	 Normal
 Other (Specify) _____	
7. Were there any perineal warts on external genital exam? Yes No
If yes, specify
 - a. Size _____ mm
 - b. Number of warts _____
 - c. Location of warts _____
8. Did the cervix appear abnormal on gross pelvic exam? Yes No
If yes, tick all that apply

 Abnormal discharge	 Warts
 Bleeds easily on touch	 Cervicitis
 Visible lesion	 Condylomata

- Bloody discharge Ulcers
- Fungating mass
- Leukoplakia Cervical polyp
- Bartholian cysts Blisters
- Overt cervical cancer Other abnormality, specify

9. Did you palpate the uterus? Yes No
If yes, then specify

- a. Estimated uterine size ___ . ___ cm
- b. Was the uterus tender? Yes No
- c. Were there possible fibroids? Yes No

10. Was there any adnexal tenderness? Yes No
If yes, specify location Right Left Both

C: Pap

11. Were you able to take an adequate Pap smear? Yes No

- a. If no, specify why
- Patient discomfort
- Excessive bleeding
- Excessive discharge or inflammation
- Other, specify

D: DIAGNOSIS

12. Normal exam Yes No
13. Candidiasis Yes No
14. Cervicitis Yes No
15. Pelvic inflammatory disease Yes No
16. Vulval warts Yes No
17. Vaginal warts Yes No
18. Genital ulcerations Yes No
19. Lower genital tract infection Yes No
20. Other Yes No
If others, specify

E: OTHER

21. Did you give any treatment to the participant? Yes No
If yes, specify (treatment)

22. Did you give referral to the participant? Yes No
If yes, specify (diagnosis and referral institution)

23. Comment.

COLPOSCOPY

Study ID Number ___ ___ ___

Interviewer Number ___ ___

Date of interview (day/month/year) ___ ___ / ___ ___ / ___ ___ ___ ___

Visit (tick one) Initial Visit Month 6 FU Month 12 FU Month 18 FU Month 24 FU LSIL FU CIN 1 FU Other, specify _____

A: PAP SMEAR DIAGNOSIS

1. What date was the Pap smear performed?
2. What was the Pap smear diagnosis (tick all that apply)?
 - No dysplasia (NIL)
 - ASCUS
 - LSIL (CIN 1)
 - HSIL (CIN 2 & 3)
 - ASC-H
 - Invasive carcinoma
 - ACG (Atypical Glandular Cells)
 - Cervicitis
 - Yeast infection
 - Indeterminate/insufficient sample
 - Other, specify _____
 - Unknown, specify reason _____
3. Is cervical biopsy with colposcopy indicated based on Pap smear cytology?

Yes No

If no, [skip to Q24 and](#) fill exit form where necessary

If yes, and colposcopy had been done previously, skip to Q24.

If yes and colposcopy had not been done previously, do a pregnancy test

4. Result of pregnancy test: Pregnant Not Pregnant

(If pregnant fill exit form, If not pregnant refer for colposcopy)

Not pregnant

B: PHYSICAL EXAMINATION

5. Temperature ___ °C

6. Is there inguinal node enlargement Yes No

7. Is there abdominal tenderness Yes No

8. Are there any abdominal masses Yes No

9. Were there any other abnormalities found on general physical exam Yes No
If yes, specify

C: PELVIC EXAMINATION

10. What was found on the external genital exam (tick all that apply)?

Abnormal visible discharge at introitus Ulcers

Excoriations Vesicles

Oedema Papules

Sores Normal

11. Were there any perennial warts on external genital exam? Yes No
If yes, specify

d. Size ___ mm

e. Number of warts ___

f. Location of warts _____

12. Did the cervix appear abnormal on gross pelvic exam? Yes No
If yes, tick all that apply

Abnormal discharge Warts

Bleeds easily on touch Cervicitis

Visible lesion Condylomata

Bloody discharge Ulcers

Fungating mass

Leukoplakia Cervical polyp

Blisters

Overt cervical cancer

13. Did you palpate the uterus? Yes No
If yes, the specify

a. Estimated uterine size ___ . ___ cm

b. Was the uterus tender? Yes No

c. Were there possible fibroids? Yes No

d. Was there any adnexal tenderness? Yes No

d(i) If yes, specify location Right Left Both

D: COLPOSCOPIC BIOPSY

15. Did you see the entire squamocolumnar junction (SCJ)? Yes No

16. Was it a satisfactory colposcopy? Yes No

If no, specify

17. Were there colposcopic findings within the transformation zone? Yes No
If yes, specify (tick all that apply)

Flat acetowhite epithelium

Micropapillary or microconvoluted acetowhite epithelium

Leukoplakia

Punctation

Mosaic

Atypical vessels

Iodine-negative epithelium

Lesion extended into endocervix

18. Draw SCJ (acetowhite, punctation, mosaics, atypical vessels, and other lesions):

19. Were there any other colposcopic findings? Yes No

If yes, specify (tick all that apply)

Mucosal bleeding easily induced

Purulent cervicitis

Opaque discharge

Yellow discharge

Other, specify:

20. Were there colposcopic findings consistent with invasive carcinoma?
Yes No

E: COLPOSCOPY DIAGNOSIS

21. Is patient eligible for cryotherapy if necessary? Yes No
If no, indicate reason (tick all that apply)

- Lesion >75% of cervix
- Lesion is larger than cryoprobe tip
- Lesion suspicious for cancer
- Polyp or anatomic defect preventing access to cervix
- Previous treatment with cryotherapy in this study
- Other, specify

22. What was your diagnosis based on colposcopy examination (tick all that apply)?

- Normal colposcopic findings
- Unsatisfactory, specify:
- Inflammation/infection, specify
- Leukoplakia
- Condyloma
- LSIL (CIN 1)
- HSIL (CIN 2 & 3)
- Invasive cancer
- Other, specify:

D: SPECIMEN COLLECTION

23. Was a biopsy taken? Yes No
- a. If yes, how many biopsies were taken ___
 - b. Draw: (mark site(s) with an 'X' on colposcopy drawing)
 - c. If no, specify why biopsy was not taken

E: Treatment

24. Was any treatment given to the patient? Yes No
If yes, specify treatment
25. Was a referral given to the patient? Yes No
If yes, specify diagnosis, and the referral institution

26. Comments:

RANDOMIZATION

Study ID Number _____ Hope ID Number _____

Randomization Number __ Interviewer Number _

Date of interview (day/month/year) ____/____/____

A: CURRENT MEDICAL HISTORY

1. Do you have pain when passing urine? Yes No Other, specify Refused Don't know
2. Do you have any lower abdominal pain? Yes No Other, specify Refused Don't know
3. Do you have any abnormal vaginal discharge? Yes No Other, specify Refused Don't know
4. Have you noticed any growths around your vagina? Yes No Don't know Other, specify Refused Don't know

B: REPRODUCTIVE HEALTH

5. How old were you when you had your first menstrual period? ____ Don't know refused Other, specify
6. Date of last menstrual period (day/month/year) ____/____/____ Don't know refused Other, specify
7. Do you have history of abnormal vaginal bleeding Yes No Don't know Refused Other, specify

If yes specify the type of bleeding

- Irregular
- Heavy
- Menorrhagia Other, specify
- Don't know
- Refused

8. Have you ever used any form of family planning method? Yes No
Don't know

Refused

Other, specify _____

If yes, specify (tick all that apply)

Injectable IUCD Natural

Condoms OCP Norplant/ Implant

BTL others, specify _____

9. Are you using any form of family planning method now?

Yes No Don't know Refused

Other, specify _____

If yes, specify (tick all that apply)

Injectable IUCD Natural

Condoms OCP Norplant/ Implant

BTL others, specify _____

10. How many times have you been pregnant? ___ ___ Refused Don't know
Other

11. How many times have you had live births? ___ ___ Refused Don't know
Other

12. How many abortions, miscarriages, and/or stillbirths have you had? ___ ___
Refused Don't know Other

13. Have you ever been admitted to the hospital with a gynecological problem?
Yes No Don't know Refused Other, specify

14. Have you ever had abdominal surgery? Yes No Refused
Don't know Other, specify

15. Have you ever had vaginal surgery? Yes No
Refused Don't know Other, specify

16. Do you currently smoke cigarettes Yes No
Refused Don't know Other, specify

C: HIV HISTORY

17. When were you diagnosed as having HIV? (day/month/year) ___ ___ / ___
___ / _____

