suggestive of cervical carcinoma (i.e. high grade intra-epithelial lesions) will undergo colposcopy with biopsy, and may potentially be eligible for randomization upon confirmed histology results. If a subject with high grade intraepithelial lesions detected on study-related Pap smears is later found to have normal or ASCUS on a follow up Pap smear (study related or not) that occurs prior to or in lieu of a colposcopic evaluation, the subject will still be required to have a study related colposcopy and biopsy.

Subjects who have biopsy-confirmed CIN 2, 3 or CIS will be eligible for the randomization and treatment portion of the study. They will be presented with the consent information upon receipt of biopsy result. Subjects with biopsy results suggestive of cervical carcinoma will be exited from the study and referred for further evaluation and management at KNH. Subjects with CIN I biopsy results will be asked to return to the clinic for repeat Pap smear in 6 months and will remain in the study. If a subject receives three consecutive CIN I histology results, she will be offered LEEP treatment by the study doctor. These participants will be treated and followed the same as other non-randomized LEEP participants.

Of note: Women with normal or with ASCUS Pap smear results (that are exited from the study) will be referred for subsequent cervical screening follow-up at the Hope Center Cervical Cancer Screening Program (CCSP). This program is administered by the Coptic Hospital and is supported by the Coptic Mission, PEPFAR, and other donor funding. The CCSP offers free cervical cancer screening to HIV-positive women enrolled in the Coptic Hope Clinic. Currently, a single visit ‘screen-and-treat’ strategy for cervical cancer prevention and treatment will be used. The screen-and-treat method involves visual inspection of the cervix followed by treatment of precancerous lesions by cryotherapy at the same visit. Patients who cannot be treated with cryotherapy are referred to KNH for subsidized cervical

care and treatment. As all study subjects are drawn from the Coptic Hope HIV clinic, they are all eligible to be screened, treated, and followed at the CCSP.

If a woman exited from her normal or ASCUS Pap smear result prefers to rescreen with the study, she may be re-enrolled using the re-enrollment consent form.

Study Procedures

1. SCREENING visit (at least 2,400 patients) (see Study Flow Diagram I, Enrollment)

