The sample size was calculated to detect a 10% difference in treatment outcomes between LEEP and cryotherapy (4% versus 14%)²⁶ with 80% power and a 0.05 significance level. Accounting for the possibility of a 20% loss-to-follow-up rate over two years, we estimated that 400 women with high grade lesions would need to be enrolled in the study with 200 women randomized to each arm. It is estimated that 200 women in each arm will allow detection of a 0.25 log₁₀ HIV virus level difference in cervical shedding between the two arms with greater than 90% power. Based on results from an ongoing cervical cancer screening study implemented at the Hope Center in 2009, our estimation of the prevalence of high-grade intraepithelial lesions is about 18%. Given this estimate and the number of women who are likely to be eligible for randomization, we calculate that we need to enroll 2,400 women for initial screening.

The primary analysis of the study will be to compare treatment outcomes between the LEEP and cryotherapy intervention arms in an intent-to-treat analysis. Treatment outcomes will be measured by Pap smears taken every 6 months during two-year follow-up. Pap smears demonstrating high-grade intraepithelial lesions will be considered positive and compared against negative or low-grade intraepithelial lesions. A Chi-square test will be used to compare the percentage of positive Pap smears between the intervention arms at 6, 12, 18, and 24 months. Secondary analyses will compare cervical HIV-1 RNA viral shedding between the treatment arms. A comparison of the average area under the curve (AAUCMB) of long-transformed HIV-1 RNA cervical viral loads will be performed between the two arms using an analysis of covariance (ANCOVA) model.

Our analysis will include contraceptive history as a potential confounder. While there has been some suggestion in the literature that HIV infectivity among women on oral

contraceptives is increased,^{33, 34} a recent study from the UW did not show a significant increase in levels of HIV RNA in cervical samples obtained from women on hormonal contraception.³⁵ A more recent multicenter randomized controlled trial performed in Asia and Africa also did not find an association between hormonal contraceptive use and increased HIV transmission.³⁶ However, increased viral shedding due to hormonal contraceptive use remains an important and interesting question and one that we will examine in our study.

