The analysis will control for immunological status through measurement of CD4 count as well as presence of and duration on antiretroviral medications. Given that the study will recruit patients from an antiretroviral treatment clinic, it is expected that the majority of subjects will be on antiretroviral medications (~75%). Type and duration of antiretroviral drugs (ARVs) will be obtained through accessing clinical medical files and CD4 count measurements will be obtained regularly during study follow-up. The impact of ARVs on recurrence of cervical intraepithelial lesions is unclear and may have minimal effect.^{37, 38} Also, despite ARV use, HIV shedding has still been detected in the genital tract.³⁹ Therefore, we are confident that the sample size will still be adequate to detect differences between treatment modalities among women on antiretroviral medications.

Data Management

Introduction

Data will be captured on paper forms or electronically using Open Data Kit (ODK) application which has a data collection component to be used on a mobile device, and a centrally managed data store component. ODK is supported by the University of Washington (UW). Data will be cleaned, and analyzed at UW project offices located at KNH in Nairobi, Kenya. This office, which supports several UW studies, will provide administrative and database management support to this research project. Study data will be collected separately from Hope clinic data and will not be linked to the Hope dataset. The forms have been used in a recent cervical screening study and improvements have been made as a result. Analysis of the data will be conducted using SPSS version 16.0 (SPSS Inc, Chicago, Illinois, USA) by UW statisticians and epidemiologists associated with the study. Data will be managed by the Data Manager and the data clerk.

See Appendix B for data collection forms

Facilities

Cervical Cancer Screening room at Coptic Hope Center for Infectious Diseases

The on-site facilities available for cervical cancer screening include two examination beds, one office desk, and one computer, and at least one tablet PC. Electronic and paper data collection forms and paper informed consent forms will be administered here. The address and intake form, which captures patient identifier data will be completed on paper forms only.

UW study clinic and laboratory at Coptic Hope Center for Infectious Diseases

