5. When was the biopsy processed? (day/month/year) ____/____/____
6. When was the biopsy reported? (day/month/year) ____/____/____
7. Was the amount of sample adequate for reading? F Yes F No Other, specify
8. What was the histology result of the cervical biopsy (tick one)?
 - No dysplasia (NIL)
 - CIN 1
 - CIN 2
 - CIN 3
 - Invasive carcinoma
 - Indeterminate/
 - CIS
 - Other, specify
9. Was there evidence of cervicitis? F Yes F No Other, specify
10. Who read the biopsy and gave this histology result?
Pathologist Interviewer number _____

11. Comments:

ENDOCERVICAL CURETTAGE HISTOLOGY REPORT

First read Re-read 1 Consensus reading Tie-break

Study ID Number _____

Hope ID Number _____

Test/ Visit code _____

Visit (tick one) Initial Visit Month 6 FU Month 12 FU Month 18 FU

Month 24 FU Other, specify

Interviewer number --- ----Patient Age _____

1. Date sample was collected in clinic (day/month/year) ____/____/____

2. Time sample was collected in clinic

3. Date sample was received in laboratory (day/month/year) ____/____/____

4. Time sample was received in laboratory

5. When was the biopsy processed? (day/month/year) ____/____/____

6. When was the biopsy reported? (day/month/year) ____/____/____

7. Was the amount of sample adequate for reading? F Yes F No Other, specify

8. What was the histology result of the Endocervical Curettage biopsy (tick one)?

No dysplasia (NIL)

CIN 1

CIN 2

CIN 3

Invasive carcinoma

Indeterminate/

CIS

Other, specify

9. Was there evidence of cervicitis? F Yes F No Other, specify

10. Who read the biopsy and gave this histology result?

Pathologist Interviewer number _____

11. Comments:

--

LEEP BIOPSY HISTOLOGY REPORT

First read Re-read 1 Consensus reading Tie-break

Study ID Number _____

Hope ID Number _____

Test/ Visit code _____

Visit (tick one) Initial Visit Month 6 FU Month 12 FU Month 18 FU
 Month 24 FU Other, specify

Patient Age _____ Interviewer number --- ----

1. Date sample was collected in clinic (day/month/year) ____/____/____

2. Time sample was collected in clinic

3. Notes:

4. Date sample was received in laboratory (day/month/year) ____/____/____

5. Time sample was received in laboratory

6. When was the LEEP specimen processed? (day/month/year) ____/____/____

7. When was the LEEP specimen reported? (day/month/year) ____/____/____

8. Was the amount of sample adequate for reading? F Yes F No Other, specify

9. What was the histology result of the LEEP cervical biopsy (tick one)?

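### Entry grade (CIN 2 v CIN 3/CIS) is known before treatment but is used in neither the primary comparison nor the named covariates; stratifying by it would be a modest, free improvement

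*Combined protocol and SAP*

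**What the plan says.** All references are to the combined protocol and SAP.

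- **Entry.** Study Population & Recruitment: "Subjects who have biopsy-confirmed CIN 2, 3 or CIS will be eligible for the randomization and treatment portion of the study".
- **Timing.** Under Study Procedures, item 3 (the randomisation visit), the woman receives her biopsy result at the visit where randomisation takes place, before treatment.
- **Recording.** Item 8 of the Colposcopic Biopsy Histology Report, which begins "What was the histology result of the cervical biopsy (tick one", lists CIN 2, CIN 3 and CIS as separate answers.
- **Allocation.** Study Procedures, item 3, describes a computer-generated assignment and sealed envelopes. It mentions no stratification factor.
- **Primary comparison.** Statistical Methods: "A Chi-square test will be used to compare the percentage of positive Pap smears between the intervention arms", at 6, 12, 18 and 24 months.
- **Covariates.** Statistical Methods: "Our analysis will include contraceptive history as a potential confounder" and "The analysis will control for immunological status through measurement of CD4 count as well as presence of and duration on antiretroviral medications".

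Entry grade appears in no analysis statement.

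**The concern.** The outcome is return of high-grade cervical disease, and entry grade is the baseline measure of that disease. It is complete by design, because only histology-confirmed women are randomised, and it is obtained in the same way in both arms. The named covariates describe the woman (contraception, immune status, antiretrovirals) and not the treated lesion.

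Two things are at stake, both only if grade predicts recurrence. The first is a little precision. The second is ease of interpretation should one arm happen to draw more CIN 3/CIS, since neither the stated randomisation nor the stated analysis addresses that. There is also a pre-specification point. A severity adjustment chosen after the results are known could draw on the histology of the LEEP specimen, which is taken at treatment in one arm only. How CD4, antiretrovirals and contraception enter alongside a chi-square test is a separate question.

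**Working it through.** **Inputs from Statistical Methods.** Risks of 4% (LEEP) and 14% (cryotherapy); "with 80% power and a 0.05 significance level"; 20% loss over two years; 200 women per arm. Sidedness is not stated; two-sided is assumed.

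**Assumptions, not in the documents.** CIN 3/CIS share s of 30%, 50% or 70%. Recurrence risk ratio RR, CIN 3/CIS v CIN 2, from 1 to 4 and equal in both arms. One binary outcome over two years. Simple randomisation.

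**1. The plan's own sample size.** With p̄ = 0.09,

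n = [1.96·√(2·0.09·0.91) + 0.8416·√(0.04·0.96 + 0.14·0.86)]² / 0.10² = (0.793 + 0.335)² / 0.01, which gives 128 per arm.

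128 / 0.80 = 160 per arm, or 320 in total. A continuity correction gives 147, then 184 per arm, or 368 in total. The stated 400 is not reproduced, but it errs on the safe side.

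**2. Power of the planned test.** With 200 × 0.80 = 160 evaluable per arm:

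- Expected events: 160 × 0.04 + 160 × 0.14 = 28.8.
- SE of the risk difference: √[(0.0384 + 0.1204)/160] = 0.0315.
- Power: Φ[(0.10 − 1.96·√(0.1638/160)) / 0.0315] = Φ(1.18) = 88.2%.

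**3. Variance with stratification.** In an arm with overall risk p, the CIN 2 risk is p / [(1 − s) + s·RR], and the CIN 3/CIS risk is RR times that. The stratified variance weights the within-grade binomial variances by (1 − s) and s.

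The most favourable case is s = 0.3, RR = 4, where the divisor is 0.7 + 1.2 = 1.9:

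- LEEP risks by grade: 0.0211 and 0.0842. Cryotherapy: 0.0737 and 0.2947.
- Numerator: 0.7 × 0.0889 + 0.3 × 0.2850 = 0.1477, against 0.1588 unstratified.
- Ratio: 0.930, equivalent to 160 / 0.930 = 172 women per arm, a gain of 12.

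**4. Shift from imbalance.** A 10-point difference in CIN 3/CIS share moves the raw risk difference by 0.10 × (mean CIN 3/CIS risk − mean CIN 2 risk). In the same case this is 0.10 × (0.1895 − 0.0474) = 1.42 points.

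Results over the three shares:

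| RR | Variance ratio | Power (88.2% unstratified) | Shift per 10-point imbalance, points |
|---|---|---|---|
| 1 | 1.000 | 88.2% | 0 |
| 1.5 | 0.995–0.996 | 88.3% | 0.33–0.39 |
| 2 | 0.983–0.990 | 88.4–88.6% | 0.53–0.69 |
| 3 | 0.956–0.981 | 88.7–89.3% | 0.75–1.13 |
| 4 | 0.930–0.974 | 88.9–90.0% | 0.87–1.42 |

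**5. How often such an imbalance arises.** The SD of the between-arm difference in share is √[2s(1 − s)/160], which is 5.1 points at s = 0.3 or 0.7 and 5.6 at s = 0.5. By the normal approximation, a difference above 10 points has probability 5.1–7.4%.

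**6. Simulation check.** With 40,000 runs per scenario, 160 per arm and RR of 1, 2, 3 or 4, power was 89.9–90.3% for the chi-square and 89.9–91.5% for the Cochran-Mantel-Haenszel test. The largest gain was 1.3 points, and at RR = 1 the loss was at most 0.15 points. With 9% risk in both arms, type I error was 4.7–5.1% over both tests. Simulated power sits slightly above the formula's, but the contrast between the tests is similar.

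**The case against.** The strongest reply is that nothing is broken. Under randomisation the error rate of the unstratified test already allows for chance covariate imbalance, and the simulation confirms it. Power exceeds the 80% sought. The largest shift above, 1.42 points, is under half a standard error (1.42 / 3.15 = 0.45) against a 10-point target. The documents do not report recurrence by entry grade. Lesions too large, or not fully visible, for cryotherapy are not randomised, which narrows the range of lesions, although it does not equalise grade. Counts at a single visit may also be lower than the two-year figure modelled here, which would shrink the gain. All of this stands, and it sets the size of the point.

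Four stronger readings are tempting, and the documents support none of them:

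- A reader might infer that the plan throws away material precision. The figures show at most 7% of variance and 2 points of power, under assumed prognosis.
- A reader might infer that an arm with more CIN 3/CIS is bound to show more recurrence. The documents do not say that grade predicts recurrence.
- A reader might infer that the randomisation is unstratified. The text states no factor, which is not the same as ruling one out.
- A reader might wish to add grade to the primary model. Statistical Methods specifies chi-square tests and no primary regression model.

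One practical objection shapes the fix. The biopsy form allows a first read, re-read, consensus and tie-break, and curettage and LEEP specimens have their own reports, so the reading that defines the stratum must be named. None of these arguments shows that the plan handles grade elsewhere or that stratifying does harm.

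**Conclusion.** The omission is clear: a complete pre-treatment measure of the disease under study is in neither the primary comparison nor the named covariates. The consequence is modest. With 160 evaluable women per arm, a CIN 3/CIS share of 30–70% and a risk ratio of 1–4, stratifying reduces variance by 0–7%, adds about 0–2 points of power, and removes a shift of 0–1.4 points per 10-point imbalance. An imbalance above 10 points would occur in about 5–7% of simple randomisations. Share and risk ratio are assumptions. If grade is not prognostic, essentially nothing changes. The planned test is valid and adequately powered on the plan's own inputs; the case for change is that the improvement is free and settles the severity adjustment in advance.

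**What to change.** In Statistical Methods, specify the between-arm comparison, at whichever visit or cumulative endpoint is named primary, as a Cochran-Mantel-Haenszel test with a Mantel-Haenszel risk difference, stratified by entry grade (CIN 2 v CIN 3/CIS).

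- Define grade by the colposcopic-biopsy reading on file at randomisation, not by a later re-read and not by the LEEP specimen.
- Keep the unstratified chi-square as a sensitivity analysis.
- Tabulate entry grade by arm.

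The cost is essentially one sentence in the plan and one row in the baseline table. It needs no new data, women or procedures.
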